1. Documented diagnosis of MM; specifically, relapsed and refractory
MM defined as:
• Received at least two previous therapies including LEN and a
proteasome inhibitor

	 All subjects must have documented progression during or within 60 days after their last prior therapy for MM Ability to understand the reason for and understand the special conditions of the pregnancy prevention risk minimization plan and give written acknowledgement of these Ability and willingness to comply with the special conditions of the pregnancy prevention risk minimization plan Creatinine clearance ≥ 45 mL/min (calculated using the Cockcroft-Gault equation) Platelets ≥75 × 10⁹/L for subjects in whom < 50% of bone marrow nucleated cells are plasma cells ≥30 × 10⁹/L for subjects in whom ≥ 50% of bone marrow nucleated cells are plasma cells. Exclusion Criteria Known or suspected hypersensitivity to POM, LEN, thalidomide,
	DEX or to any of the excipients 2. Subjects who are refractory (defined as progression during or within 60 days after their last days of POM) or intelerent to POM
Sample Size, Planned Total Number of Study Sites and Locations Investigational Medicinal Drug(s) (Name,	 60 days after their last dose of POM) or intolerant to POM Up to 126 subjects Up to 48 subjects for the MOR03087 monotherapy/bi-weekly escalation Up to 18 for the MOR03087 monotherapy/weekly escalation Up to 24 for the MOR03087 + DEX part (up to 18 for dose escalation cohorts and at least 6 for confirmatory cohort) Up to 18 for the MOR03087 + POM + DEX (up to 12 for dose escalation cohorts and at least 6 for confirmatory cohort) Up to 18 for the MOR03087 + LEN + DEX (up to 12 for dose escalation cohorts and at least 6 for confirmatory cohort) Up to 18 for the MOR03087 + LEN + DEX (up to 12 for dose escalation cohorts and at least 6 for confirmatory cohort) Approximately 10-15 sites in Germany and Austria MOR03087, pomalidomide, lenalidomide, dexamethasone
Description) Dose, Route of Administration, Treatment Regimen	In each cohort, 28-day cycles will be used. An independent Data Monitoring Committee (DMC) will review the relevant safety information before considering dose escalation for the next cohort. Part A: MOR03087 dose escalation (bi-weekly treatment): - Dose level 1: 0.01 mg/kg - Dose level 2: 0.04 mg/kg - Dose level 3: 0.15 mg/kg - Dose level 4: 0.5 mg/kg - Dose level 5: 1.5 mg/kg - Dose level 6: 4.0 mg/kg - Dose level 7: 8.0 mg/kg - Dose level 8: 16.0 mg/kg*

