7 STUDY DESIGN

7.1 Overall Study Design and Investigational Plan

This is an open-label, multicentre, standard 3+3 dose-escalation study designed to characterize the safety profile and to assess the preliminary efficacy of MOR03087 in adult subjects with relapsed or refractory MM as monotherapy and in combination with DEX or standard IMiD therapy (POM and LEN). Approximately 10-15 sites will participate in this study.

The MTD and/or recommended dose and dosing regimens will be confirmed in a confirmation cohort of at least 6 subjects. A total of up to 126 subjects may participate in the study (including dose escalation and confirmation cohorts).

The overall study design for the latter stages of the study is indicated in Figure 1. A study flow chart for individual subjects is provided in Figure 2.

Cohort 8 q2w 16 mg/kg (≥3pts)				
Cohort 6b q1w 4 mg/kg (≥3pts) Cohort 6c q1w 4 mg/kg +DEX (≥3pts)	Cohort 7b q1w 8 mg/kg (≥3pts) Cohort 7c q1w 8 mg/kg +DEX (≥3pts)	Cohort 8b q1w 16 mg/kg (≥3pts) Cohort 8c q1w/q2w 16 mg/kg +DEX (≥3pts)	Monotherapy Confirmation Cohort Recommended dose/schedule q2w or q1w or q1w/q2w+DEX (≥6 pts)	
		Cohort 7d 8 mg/kg q1w +POM +DEX (≥3 pts)	Cohort 8d 16 mg/kg q1w/q2w +POM +DEX (≥3 pts)	Confirmation Combo Recommended dose POM +DEX (≥ 6 pts)
		Cohort 7e 8 mg/kg q1w +LEN +DEX (≥3 pts)	Cohort 8e 16 mg/kg q1w/q2w +LEN +DEX (≥3 pts)	Confirmation Combo Recommended dose LEN +DEX (≥ 6 pts)

q2w: every 2 weeks; q1w: every week; POM: pomalidomide; LEN: lenalidomide; DEX: dexamethasone

Figure 1: Overall Study Design, Dose Levels 6, 7, 8, and Confirmation Cohorts

[figure not shown]

Figure 2: Overall Study Design, Individual Subject Treatment

MM: multiple myeloma; PD: progressive disease; SD: stable disease

Part A: MOR03087 dose escalation (bi-weekly treatment):

Up to 8 dose levels of MOR03087 will be evaluated:

- Cohort 1 Dose level 1: 0.01 mg/kg
- Cohort 2 Dose level 2: 0.04 mg/kg
- Cohort 3 Dose level 3: 0.15 mg/kg
- Cohort 4 Dose level 4: 0.5 mg/kg
- Cohort 5 Dose level 5: 1.5 mg/kg
- Cohort 6 Dose level 6: 4.0 mg/kg
- Cohort 7 Dose level 7: 8.0 mg/kg
- Cohort 8 Dose level 8: 16.0 mg/kg

Each 28-day cycle will consist of:

MOR03087 infusion on Day 1 and Day 15 of the cycle. In Cycle 1, a loading dose will additionally be administered on Day 4 of the cycle.

At least 48 hours will pass between the first study drug administration to the subjects within a cohort in order to observe for adverse events (AEs).

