Part B: MOR03087 dose escalation (weekly treatment):

- Dose level 6b: 4.0 mg/kg
- Dose level 7b: 8.0 mg/kg
- Dose level 8b: 16.0 mg/kg

Each 28-day cycle will consist of:

MOR03087 infusion on Days 1, 8, 15, and 22 of the cycle. In Cycle 1, a loading dose will additionally be administered on Day 4 of the cycle.

Part C: MOR03087 dose escalation (weekly/biweekly treatment) plus low dose of DEX:

- Dose level 6c: 4.0 mg/kg
- Dose level 7c: 8.0 mg/kg
- Dose level 8c: 16.0 mg/kg

Each 28-day cycle will consist of:

MOR03087 infusion on Days 1, 8, 15, and 22 of the cycle. In Cycle 1, a loading dose will additionally be administered on Day 4 of the cycle.

Only for dose level 8c, for cycles 4 and onwards each 28-day cycle will consist of:

MOR03087 infusion on Days 1 and 15 of the cycle.

Subjects who have received treatment beyond Cycle 3 will be switched to the biweekly schedule at the next Day 1 or Day 15 visit. In exceptional cases – and after discussion between the investigator and the sponsor – the treating physician may determine that it is in the best interest of the subject to remain on the weekly MOR03087 schedule, in which case the sponsor should be informed accordingly.

The low dose of DEX is defined as a single dose of 40 mg once to be orally administered on Days 1, 8, 15, and 22 with the exception of subjects with > 75 years of age, for whom the respective weekly dose should be reduced to 20 mg.

For subjects in Cohort 8c who switch to biweekly MOR03087 treatment from Cycle 4 onwards, the DEX treatment schedule will remain unchanged (Days 1, 8, 15, and 22).

If subjects receive glucocorticosteroids at a dose equivalent of 10 mg prednisone (see exclusion criterion #15), the total weekly dose of glucocorticosteroids must not exceed 20-40 mg of DEX per week. Total dose of DEX should be calculated in accordance with Appendix 18.7.

In Cycle 1 DEX is to be added to the loading dose on Day 4.

Following the completion of Part B dose level 6b and Part C dose level 6c, and taking into account available safety information from Part A dose level 8, the DMC will provide recommendation if some or all of the planned weekly MOR03087 monotherapy dose escalation cohorts will be tested.

Following completion of Parts A, B, and C (dose escalation of MOR03087 bi-weekly and weekly regimen), the MTD or recommended dose and schedule will be confirmed in a minimum of 6 subjects.

Part D: MOR03087 (weekly/biweekly treatment) in combination with POM+DEX

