Following completion of Parts D and E (dose escalation of MOR03087 in combination with POM+DEX and LEN+DEX), the MTD and/or recommended dose in each part will be confirmed in a minimum of 6 subjects.

All cohorts:

After the first administration of study drug, the subjects will remain at the site until the end of Day 2 for safety monitoring. The subjects will not stay overnight at the site for subsequent administrations.

Based on the individual risk/benefit ratio, subjects who have an ongoing response of at least stable disease (SD) may continue treatment with the assigned study regimen until disease progression or until a maximum of 3 years after first treatment. In case subjects present with progressive disease or with no better status than SD after four treatment cycles starting with Cycle 1 Day 1, the investigator may add a low weekly dose of DEX to the regimen at his/her discretion, provided DEX is not already part of the treatment regimen.

At least 3 subjects meeting all inclusion and none of the exclusion criteria, as determined at the screening visit (see Sections 8.1 and 8.2) will be enrolled into each cohort.

Enrolment into a cohort at the next higher dose level will be based on the data generated from the previous dose level and guided by clinical review until

- the maximum planned dose has been reached, or
- the review of the safety data indicates a need to either expand the current dose level cohort to include 6 subjects or stop the dose escalation or the study, or
- the review of Part B dose level 6b and Part C dose level 6c, including available safety information from Part A dose level 8, indicates that only some of the planned weekly MOR03087 monotherapy dose escalation cohorts should be tested.

The DMC safety review will take place after the third subject enrolled into a cohort has undergone minimum safety evaluations (as defined for the "DLT Evaluable Population" in Section 15.1). The safety assessment will take into account AEs reported from Day 1 after the start of the first infusion through Day 29 before the start of the second cycle. The next cohort will only be started after the positive outcome of the safety assessment.

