## **15.7 Safety Analysis**

### **15.7.1 Dose Limiting Toxicities and Maximum Tolerated Dose**

One of the primary endpoints will be to determine the MTD or recommended dose and dosing regimen for MOR03087 with or without DEX and in combination with two standard IMiD therapies. This primary endpoint will be determined in the DLT Evaluable Population and will be based on a 4-week safety assessment period (one 28-day cycle).

Following completion of Parts A-C (dose escalation of MOR03087 alone and in combination with DEX using two dosing schedules), the MTD and/or recommended dose will be confirmed in a minimum of 6 subjects. Following completion of Parts D and E (dose escalation of MOR03087 in combination with POM+DEX and in combination with LEN+DEX), the MTD and/or recommended dose in each treatment arm will be confirmed in a minimum of 6 subjects.

The recommended doses for the confirmation cohorts will be determined after review of all available safety data from the corresponding dose-escalation portion of the study and based on the recommendation of the DMC. The recommended dose may be the MTD or a dose below the

MTD. Additionally, the number and percentage of DLTs will be summarized descriptively for all subjects including subjects from the confirmation cohorts receiving the recommended dose and including further cycles of MOR03087 or cycles of combination therapy. For definition of DLT see Section 8.5.

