## **15.9 Sample Size Determination**

A 3 + 3 design will be used for the dose-escalation part of the study with confirmation cohorts of 6 subjects. At least 9 subjects will be analyzed in the recommended dose groups of each part: 6 subjects from the confirmation cohort and at least 3 subjects from the dose-escalation cohort who receive the same dose and regimen and combination treatment (if applicable). This ensures that AEs that occur in a subject with a probability of 17% will be observed at least once within this group with a probability of 81%. If the AEs occur with a probability of 23%, then the probability of observing the AEs will increase to 90%.

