Subjects who have received treatment beyond Cycle 3 will be switched to the biweekly schedule at the next Day 1 or Day 15 visit. In exceptional cases, and after discussion between the investigator and the sponsor, the treating physician may determine that it is in the best interest of the subject to remain on the weekly MOR03087 schedule, in which case the sponsor should be informed accordingly.

The low dose of DEX is defined as a single dose of 40 mg or lower (as described in protocol section 7.1), once, to be orally administered on days of MOR03087 infusion.

For subjects in Cohort 8c who switch to biweekly MOR03087 treatment from Cycle 4 onwards, the DEX treatment schedule will remain unchanged (Day 1, 8, 15 and 22).

Following the completion of Part B dose level 6b and Part C dose level 6c, and taking into account available safety information from Part A dose level 8, the DMC will provide recommendation if some or all of the planned weekly MOR03087 monotherapy dose escalation cohorts will be tested.

Following completion of Parts A, B, and C (dose escalation of MOR03087 bi-weekly and weekly

regimen), the MTD or recommended dose and schedule will be confirmed in a minimum of 6 subjects.

Part D: MOR03087 (weekly/biweekly treatment) in combination with POM+DEX

- Dose level 7d: 8.0 mg/kg
- Dose level 8d: 16.0 mg/kg

Each 28-day cycle will consist of:

MOR03087 infusion on Days 1, 8, 15, and 22 of the cycle. In Cycle 1, a loading dose will additionally be administered on Day 4 of the cycle.

Only for dose level 8d, for cycle 4 and onwards each 28-day cycle will consist of: MOR03087 infusion on Day 1 and 15 of the cycle.

Subjects who have received treatment beyond Cycle 3 will be switched to the biweekly schedule at the next Day 1 or Day 15 visit. In exceptional cases, and after discussion between the investigator and the sponsor, the treating physician may determine that it is in the best interest of the subject to remain on the weekly MOR03087 schedule, in which case the sponsor should be informed accordingly.

Oral POM 4 mg on Days 1-21 of the 28-day cycle.

Oral DEX 40 mg (\leq 75 years old) or 20 mg ($>$ 75 years old) on Days 1, 8, 15, and 22 of the 28-day cycle.

For subjects in Cohort 8d who switch to biweekly MOR03087 treatment from Cycle 4 onwards, the DEX treatment schedule will remain unchanged (Day 1, 8, 15 and 22).

In Cycle 1 DEX is to be added to the loading dose on Day 4.

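### The promised 9 subjects per recommended dose group, and the 81%/90% AE detection built on them, are assured in only three of the five parts, because Parts A, B and C share one confirmation cohort

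*Protocol*

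**What the plan says.** Protocol 15.9 states: "At least 9 subjects will be analyzed in the recommended dose groups of each part". It builds the 9 from 6 confirmation subjects and at least 3 escalation subjects who had the same dose, schedule and co-medication. It then claims: "AEs that occur in a subject with a probability of 17% will be observed at least once within this group with a probability of 81" per cent, rising to 90% when the AE rate is 23%. SAP 5 repeats the 9-subject sentence without the probabilities.

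The design sections describe confirmation differently:

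- **Parts A, B and C together.** Protocol 7.1 says that after these three parts "the MTD or recommended dose and schedule will be confirmed in a minimum of 6" subjects. SAP 3.1 has the same rule, and Protocol 15.7.1 and SAP 10.1 agree. Figure 1 of the protocol shows a single box for this cohort, with its content left open: "Recommended dose/schedule q2w or q1w or q1w/q2w+DEX".
- **Parts D and E.** Each has its own confirmation. Protocol 15.7.1 says the "recommended dose in each treatment arm will be confirmed in a minimum of 6 subjects".
- **Escalation cohorts.** Protocol 7.1 enrols in each cohort "At least 3 subjects meeting all inclusion and none of the exclusion criteria", with expansion to 6 allowed.
- **Subject budget.** The synopsis lists Part A as "Up to 48 subjects for the MOR03087 monotherapy/bi-weekly escalation" and Part B likewise as escalation only. Confirmatory places appear only under the DEX, POM and LEN parts (C, D and E).

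Protocol 15.1 treats A to E as five treatment arms and plans recommended-dose summaries for each of them. Protocol 15.3, 15.4 and 15.7.2 attach exact 95% intervals to the recommended dose group of each arm. SAP 7.2 plans recommended-dose tables for C, D and E only.

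**The concern.** The sample size sections speak of every part, while the design supplies one confirmation cohort for three of the five. Confirmation subjects can be pooled only with escalation subjects on an identical dose, schedule and combination. Parts A (every two weeks), B (weekly) and C (with DEX) differ in exactly those respects, so the 6 shared subjects can be added to only one of them.

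The detection statement is the only quantitative justification that Protocol 15.9 gives for the group size, and AE incidence is a primary endpoint of this first-in-human study. A reader who takes 15.9 at face value would credit two parts with a chance of seeing an AE that the design does not assure.

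**Working it through.** **Inputs.** AE rates of 17% and 23%, stated detection of 81% and 90%, and n = 6 + 3 = 9 come from Protocol 15.9. Escalation cohort sizes of 3 (assured) and 6 (expanded) come from Protocol 7.1. The subject budget comes from the protocol synopsis.

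**Step 1: reproduce the plan's figures.** The probability of at least one event in n subjects is 1 − (1 − p)^n.

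- p = 0.17, n = 9: 1 − 0.83^9 = 0.813 (stated 81%)
- p = 0.23, n = 9: 1 − 0.77^9 = 0.905 (stated 90%)

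Both reproduce.

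**Step 2: which parts reach 9?** D and E each have 6 + 3 = 9. Of A, B and C, the one whose regimen is chosen for the shared cohort has 6 + 3 = 9. The other two have no confirmation subjects, so an opened dose level there is assured 3, or has 6 if expanded.

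**Step 3: detection at those sizes.**

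| n | AE rate 17% | AE rate 23% | AE rate needed for 81% | AE rate needed for 90% |
|---|---|---|---|---|
| 9 | 81.3% | 90.5% | 16.9% | 22.6% |
| 6 | 67.3% | 79.2% | 24.2% | 31.9% |
| 3 | 42.8% | 54.3% | 42.5% | 53.6% |

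The last two columns use 1 − (1 − q)^(1/n), where q is the target probability.

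**Step 4: check against the budget.** With 6 subjects at every dose level, escalation takes A 8 × 6 = 48, B 3 × 6 = 18, C 3 × 6 = 18, D 2 × 6 = 12 and E 2 × 6 = 12, which totals 108. Three confirmation cohorts add 3 × 6 = 18, and 108 + 18 = 126, the stated maximum. The budget was therefore drawn up for three confirmation cohorts. The two mentioned in the synopsis under Design and Methodology would give 108 + 12 = 120.

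**The case against.** The best defence is that the sentence defines its own group. A recommended dose group consists of confirmation subjects plus matching escalation subjects, so a part without a confirmation cohort has no such group and the probabilities are true wherever one exists. One dose and schedule is selected from A to C, and the Data Monitoring Committee may leave some Part B levels unopened. SAP 7.2 already confines recommended-dose tables to C, D and E, and no test or dose decision uses 81% or 90%.

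Much of this stands. The practical effect is small, and the SAP's table plan fits the design. But the self-defining reading conflicts with the words *each part*, and with the recommended-dose summaries that Protocol 15.1, 15.3, 15.4 and 15.7.2 promise for each treatment arm. SAP 7.2 shows that the sample size text was not brought into line; it does not correct that text.

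A reader might also infer three stronger points that the documents do not support:

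- **That exact intervals will be reported on 3 or 6 subjects in a recommended dose group of Part A or B.** SAP 7.2 gives intervals only for combined presentations, rules them out by dose level, and plans no recommended-dose table for A or B.
- **That the maximum of 126 rules out one confirmation cohort per part.** Five cohorts would need 108 + 30 = 138 only if every dose level were expanded to 6. With 3 at each of the 18 levels, the total would be 54 + 30 = 84. The shared cohort follows from the design text, not from the cap.
- **That the primary endpoint requires a confirmation cohort for monotherapy and another for the DEX combination.** Protocol 11 asks that a maximum tolerated or recommended dose be determined in each setting. It promises no confirmation cohort for each.

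**Conclusion.** The statement is wrong in scope and right in arithmetic. At least 9 subjects, and with them 81% and 90% detection, are assured in three of the five parts: one of A to C, plus D and E. In the other two, detection at an opened dose level is 43% and 54% with 3 subjects, about 38 and 36 percentage points below the stated figures. If the level is expanded to 6 it is 67% and 79%, about 14 and 11 points below.

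This rests on reading *part* as one of the five named parts, on the pooling rule as written, and on assured numbers. Replacement of non-evaluable subjects could add to a safety count but is not guaranteed. The consequence is a misstated safety-detection claim. No analysis, dose decision or planned SAP table is affected.

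**What to change.** 1. **Protocol 15.9:** limit the 9-subject statement and the 81%/90% figures to the parts that receive a confirmation cohort (one of A to C, plus D and E). State 43%/54% (3 subjects) and 67%/79% (6 subjects) for a dose level without one.
2. **SAP 5:** limit the 9-subject sentence in the same way, consistent with SAP 7.2. It states no probabilities, so nothing else changes there.
3. **Protocol 15.1, 15.3, 15.4 and 15.7.2:** align the references to each treatment arm's recommended dose group with that limit.
4. **Protocol synopsis, Design and Methodology:** reconcile the two confirmation cohorts given there with the three in Figure 1, the synopsis sample size and Protocol 15.7.1.

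The cost is wording only. No subjects are added, and no decision rule or SAP table changes. The one drawback is that the protocol would show less favourable detection figures for the parts without a confirmation cohort.

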## **15.10 Significance Level**

Confidence intervals, both individual and simultaneous, will be at the 95% confidence level unless stated otherwise.

## 15.11 Procedures for Missing, Unused, and Spurious Data

Missing values will not be substituted by estimated values, but treated as missing in the statistical evaluation. All data from all subjects dosed in the study will be included in all listings, plots, summary tables, and statistical analyses when appropriate.

## **15.12 Rules for Excluding Subjects from Analysis**

All dosed subjects will be included in the analyses unless otherwise specified. The sponsor will make any decisions regarding whether any subjects will be excluded from the evaluations when the protocol violation is considered to have a negative impact on the scientific aspects and interpretation of the study results. If the subject has received any IMP, all available safety data will be used. The reason(s) for any exclusion will be described in the report.

## 15.13 Procedures for Reporting Deviations from Original Statistical Plan

Any deviations from the statistical analysis outlined in this protocol will be described, and reasons for the deviations listed, in the final clinical study report.

# **16 SPECIAL REQUIREMENTS AND PROCEDURES**

## 16.1 Institutional Review

Before starting this study, the protocol (authorized by the sponsor) will be submitted to the regulatory bodies/local health authorities (in accordance with local regulations) and to the IEC/IRB for evaluation. The protocol will also be signed by the principal investigators before submission to the IEC/IRB. The study will not start in the concerned Member State before the respective IEC/IRB gives written approval or a favorable opinion in accordance with ICH E6 GCP and all applicable regulatory bodies/local health authorities give approval or a favorable opinion as required.

No substantial changes to the final approved (authorized) protocol will be initiated without the IEC's/IRB's prior written approval or favorable opinion of a written amendment, except when necessary to eliminate immediate hazards to the subjects or when the change involves only logistics or administration. The sponsor will authorize and the principal investigator(s) will sign the protocol amendment prior to submission to the IECs/IRBs. Protocol amendments should be submitted to the IEC/IRB without delay. Any significant deviation from the protocol when no approved amendment exists will be regarded as a protocol violation, and will be addressed as such during the reporting of the study.

